a) If not in the protocol, or in response to other questions (e.g. Radiation Safety) add here. Be sure to remain compliant with NYS laws around genetic testing and the use of research tests, as only FDA or NYS DOH approved tests from CLIA labs can be used to guide clinical decision making. If results are not being returned, explain the rationale.

See below.

b) Specify which results will be returned to subjects and/or their clinical care team. If results are not being returned, explain the rationale.

Results are not being returned to subjects and/or their clinical care teams. Results of spirometry will not be shared with the participants as they were not administered by a respiratory technician or physician and they are not clinically relevant. The blood tests collected for this study are for research purposes only and are not clinically relevant.

c) How and when will subjects be informed of the study results? The PPHS expects proactive outreach by the study team.

Study results will not be communicated with study participants as part of the study so as not to influence decision making.

15. External IRB Review History

If you have previously submitted this protocol for review by an external IRB (non-Mount Sinai IRB), provide the name of the reviewing IRB and the associated project identification number. Please include the details of the review with appropriate documentation including the date of review and the IRB contact information.

N/A

16. Control of Drugs, Biologics, or Devices:

a) If not included in the protocol, the supplemental questions of the Investigational Drug service or included in other uploaded documents please add here:

N/A

- *If the Human Research involves drugs, biologics, or devices, describe the plans to store, handle, and control those drugs, biologics or devices so that they will be used only on subjects and be used only by authorized investigators. This very well may involve OR personnel, nursing, central sterilization and supplies etc. The plan should be comprehensive and robust.*

- *Note: If there are required departmental policies that regulate the control of drugs, biologics, or devices, provide that information here.*

 Mount Sinai	Protocol Name:	Obesity and Asthma: Unveiling Metabolic and Behavioural Pathways
	Principal Investigator:	[name], DrPH
	Primary Contact Name/Contact Info:	[name] / [contact] / [contact]
	Date Revised:	1/25/21
	Study Number:	STUDY-16-00079

- *Note: For studies involving research drugs or biologics, you will need to obtain the approval of Investigational Drug Service (IDS) of the Mount Sinai Pharmacy, regardless of whether you will be utilizing the IDS to manage the control of research drugs and biologics.*

Obesity and Asthma: Unveiling Metabolic and Behavioral Pathways

Statistical Analysis Plan

PI: [name], DrPH

NCT04113746

Document Date: 8-12-2015

**Data Analyses:** We will obtain a HIPAA waiver to use de-identified data to compare non-respondents and those lost to follow-up to study participants by age, gender and ethnicity. **Factor Structure of Measures:** We will examine the factor structure of key measures (e.g., MARS) and the multi-component structure of the IPQ and BMQ. **Measurement Invariance:** We will determine whether the key measures are invariant across language using multiple indicator multiple cause models. We will use the chi-square test, ANOVA, or the Kruskal Wallis test to compare the baseline characteristics of obese vs. non-obese patients with early onset and late onset asthma, as appropriate. **Overview:** We will employ latent growth curve modeling (LGCM) approaches using MPLUS 7.3 software to test Aims 1 and 2 hypotheses. LGCM leverages the analytical power of structural equation modeling (SEM) for the intensive analysis of longitudinal data. Similar to classic SEM, LGCM allows for the examination of complex models including those that posit mediation and moderation, as proposed here. Before conducting analyses, we will examine the distribution of dependent variables and, as appropriate, consider transformations (e.g., log, Box-Cox) to reduce non-normality in continuous variables.

**Aim 1.** Compare the longitudinal relationship between L-arginine/ADMA balance and morbidity (lung function, asthma control, acute resource utilization, and quality of life) between obese adults with late onset asthma vs. (1) obese adults with early onset asthma and non-obese asthmatics with early (2) or late (3) onset disease:

The primary asthma morbidity outcomes will be FEV1 and control (ACQ scores); the primary measure of NO metabolism will be L-arginine/ADMA ratio. All analyses will compare four groups: 1) obese with late onset asthma; 2) obese with early onset asthma; 3) non-obese with late onset asthma; and 4) non-obese with early onset asthma. First, we will compare the levels of plasma L-arginine, ADMA, L-arginine/ADMA ratios, and arginase among these groups, at each time point using the Kruskal-Wallis test. The Wilcoxon signed-rank test will be used to compare levels of NO metabolism biomarkers in periods without vs. during asthma attacks. The analysis will involve longitudinal assessment of asthma morbidity measures across four time points (0, 6, 12, and 18 months). We hypothesize that both time-varying covariates (e.g., NO metabolism biomarkers) assessed at the four time points and time-invariant covariates (e.g., early vs. late asthma onset) will predict asthma morbidity assessed at these time points (Figure 1). We also hypothesize potential lagged effects of covariates at earlier time points. As a first step, we will identify the measurement model for the latent variables at each time point using confirmatory factor analysis. Specifically, we will create latent variables representing random effects intercepts and slopes for NO metabolism (NOt0, NOt6, NOt12 and NOt18; where t0 represents baseline NO metabolism biomarkers) and asthma morbidity measures (AMt0, AMt6, AMt12 and AMt18; e.g., FEV1 at baseline, 6, 12, and 18 months). We will estimate slope and intercept parameters using a Weighted Least Squares Mean-Variance adjusted (WLSMV) estimator, which provides robust estimates for complex models with modest sample sizes and can be employed with dichotomous, ordinal, and/or continuous endogenous variables. We will test this measurement model for absolute fit using Chi-square and RMSEA statistics. In addition, we will consider adjusting the model based on modification indices to improve the overall fit.

Next, an overall unconditional model will be fitted to identify the growth trajectory across time. To that end, we will fit a growth function for NO metabolic biomarkers and asthma morbidity (e.g., FEV1) using linear, quadratic, and unstructured models. Relative model fit will be evaluated based on various indices of exact and close fit:  $\chi^2$  (>.05), the comparative fit index (CFI>.97), the Tucker-Lewis fit index (TLI>.97), the root mean squared error of approximation (RMSEA<.05), and the weighted root mean square residual when using WLSMV (WRMR<.90). The most parsimonious model with the best fit will be retained. Finally, we will fit the full structural model, including the hypothesized relationships. For example, obesity and age of onset will be included as a predictor of NO metabolism-related pathways as well as asthma morbidity. Because we hypothesize that NO metabolism-related pathways are primarily important for obese patients with late onset asthma, we will include an interaction term between obesity and age of asthma onset. The model will also control for sex, age, comorbidities (including OSA), depression, allergic sensitization, and other key baseline covariates. To address the possible mediational effects of NO metabolism-related pathways, we will fit models to estimate both direct and indirect effects, first separately, and then combined. Lagged effects of the time- varying predictors, as well as the effects of the latent growth variables themselves (intercept, slope, and their random effects) will be evaluated as potential mediators (i.e., NO metabolism biomarkers) of the effects of obesity and age of onset on asthma morbidity. We will also be able to compare models of complete vs. partial mediation by comparing constrained models (direct effects constrained to zero) with unconstrained models that allow for partial mediation. Relative fit, as well as estimates of effect size will be calculated, along with Sobel tests and Monte Carlo confidence intervals to evaluate the mediational hypotheses. As indicated above, the interrelationships between gender, obesity, and asthma morbidity is complex, thus, we will explore the potential modifying effects of gender. We will also conduct sensitivity analyses in which we test different thresholds for the definition of good medication adherence (≥70%, 60%, 50%). Once the final model is fitted, we will repeat the analyses freeing the parameters to differ by gender. Comparing these models to a model in which the differential effects of gender are constrained will provide valuable insight into the possible role of

gender in the hypothesized effects.

[figure not shown]
**Note:** In addition to data from the 4 scheduled time points, we will also obtain data when patients have asthma exacerbations. Because LGCM is limited in its ability to model effects in which time points are not common throughout patients (as anticipated for exacerbation data), we will use more flexible hierarchical growth models (e.g., linear mixed models or generalized linear mixed models) as needed to explore these data points.

**Aim 2.** Evaluate the interrelation between obesity- and asthma-related illness beliefs, and the impact of cognitive function, on patients' management of these conditions over time: For asthma, we will compare electronic (primary outcome) and self-reported (secondary outcome) adherence to medications according to obesity/age of onset categories using a chi-square test. For obesity, primary outcomes will be the Connor Diet Habit Survey scores for diet and accelerometer data for exercise. Secondary analyses will assess other SMB.

We will use LGCM to examine the interrelationships between asthma- and obesity-related beliefs and self-management of these conditions over time (Figure 4). Latent variables to be investigated include: 1) cognition, as measured by the battery described above; 2) asthma beliefs; 3) obesity beliefs. Asthma and obesity beliefs will constitute a latent variable consisting of two constructs: a) disease beliefs (measured with the IPQ) and b) medication/diet/exercise beliefs (measured with the BMQ); and 3) asthma and obesity SMB, including time-variant medication adherence (electronic and self-report measures following each study time point), diet, exercise and other SMB. We will use LGCM to predict the effects of obesity on these latent behavioral constructs. We will be able to examine the direct and indirect pathways from obesity to cognitive functioning and illness beliefs, to asthma and obesity SMB (intercept, slope, as well as their random effects). We will assess the potential influence of cognition and illness beliefs on SMB separately then test a full model, predicting SMB once individual contributions are identified. As in Aim 1, we will estimate both direct and indirect effects, as well as partial vs. complete mediation. We will include covariates as above. Integrating Biological and Behavioral Pathways: Finally, we will employ LGCM to characterize the interrelation and relative contribution of biological and behavioral pathways linking obesity and asthma morbidity (Figure 1). In addition to the time-variant relationships between SMB and biological markers, we will also explore the possibility of time-lagged relationships between biological markers and SMB. For example, we will assess if SMB at time 1 predict L-arginine/ADMA ratios at time 2, and vice-versa. Comparison of model fit among these lagged analyses will yield critical new data to elucidate the complex interplay between biology and behavior in the maintenance of asthma morbidity. The model will control for other confounders as specified above.

**Missing Data:** For data missing at random (e.g., data entry errors), we will use multiple imputation methods with PROC MI and PROC MIANALYZE in SAS. For the outcome assessments, we cannot assume data are missing at random, but we will consider pattern-mixture methods to adjust for an occasional missed point in subjects who complete subsequent follow-up. **Power Calculation:** Power calculations for LGCM and sample size based were based on published methods. Effect size in this approach is defined as a null and alternative hypothesis value of the RMSEA index, which we hypothesize to be 0.05 (adequate fit) and 0.03 (good exact fit), respectively. Power in SEM can be conceptualized as a function of sample size and the number of parameters to be estimated in the model, relative to the information provided in the overall variance-covariance matrix of the observed variables. The estimated power is based on a proposed sample size of 400 with an 80% follow-up rate. For Aim 1, the proposed model involves 14 latent variables across all time points, and 34 observed underlying variables, yielding estimated power >0.80 for an average effect of 0.10 with an alpha of 0.05. For the model in Aim 2, there are 13 latent variables (not including the six separate indicators of cognition) and 18 observed variables, yielding >0.80 power for average effects of 0.15. Overall, despite the challenges of estimating *a priori* power for SEM approaches, especially those involving growth models, we believe the proposed study will be adequately powered to address the research aims.

**Aim 3.** Develop and pilot test three theory-based modules that integrate counseling for asthma and obesity to promote better SMB, including self-monitoring, adherence to asthma medications, and lifestyle changes for weight loss: **Overview:** We will script messages aimed to counter beliefs linked to low adherence to asthma and obesity SMB and to support those that promote better SMB. We will incorporate these messages in 3

counseling modules: a session in which the counselor identifies the patient's beliefs about asthma and obesity and provides education to address them, then 2 sessions in which we integrate these messages with diet and physical activity counseling from the Diabetes Prevention Program (DPP). After pre-testing and refinement, we will conduct a proof-of-concept pilot RCT of the modules in a subset of 80 obese patients who have completed their 18-month participation in the observational cohort portion of this study. We recognize that effective self-management of asthma and obesity requires complex behaviors and thus a more comprehensive intervention than what we propose here. As such, we do not anticipate a major impact of the modules on SMB. However, if the modules are well received by patients and results of the RCT suggest a positive influence on beliefs and behaviors, we will seek additional funding to elaborate this approach to integrated asthma-obesity self-management support and create then test a fully developed intervention.

**Translating Aim 2 Findings to an Integrated Asthma-Obesity Self-Management Counseling Strategy:** To guide design of the intervention, we will apply the SRM, which has been used to build coping strategies, knowledge, and skills in patients with low adherence to self-management tasks by addressing beliefs that influence SMB. According to the SRM, behavior changes associated with positive health outcomes will counter maladaptive beliefs and provide the positive reinforcement necessary to sustain behavior change. Our quantitative analyses in Aim 2 will link asthma (disease and medication) and obesity-related beliefs, and their interrelationship, to adherence to SMB for both conditions. Illness and medication beliefs having the strongest associations with poor SMB will be addressed in the intervention. **Session 1:** As in our PCORI-funded intervention for asthma in the elderly, we will develop a practical screening tool based on validated items from the IPQ and BMQ that will be used by a counselor (described below) to identify key disease beliefs held by the patient. The counselor will then address the beliefs that may interfere with effective SMB using motivational interviewing techniques. This targeted counseling will be combined with a discussion of the interaction between asthma and obesity and benefits of integrated management (e.g., better asthma control = greater ability to do exercise = weight loss = reduced risk of asthma; dietary modification = weight loss = reduced asthma risk). **Sessions 2 and 3:** will be based on modules 2 and 4 of the DPP weight management curriculum, which focus on diet and exercise self-monitoring. We will modify each DPP module to reinforce issues addressed in session 1 and will integrate strategies for co-management of obesity and asthma. For example, in session 2, we might recommend use of controller medication immediately before a meal (e.g., breakfast) or link daily weight and diet self-monitoring tasks with peak flow measurements. We may reinforce use of short acting bronchodilators before exercise and educate patients to differentiate between asthma symptoms and shortness of breath from exertion.

We will use cognitive restructuring methods to address misconceptions about asthma and obesity. For example, patients may feel that asthma or obesity cannot be controlled, even with appropriate treatment, because they compare their functional status to peers without the illness. These views can be "reconstructed" by teaching patients to compare themselves to other patients of the same age with these conditions and to give them realistic and achievable markers for improvement over time (e.g., goal to walk 1 mile in 1 month). We will also focus on refining symptom discrimination for guiding self-regulation feedback loops. According to the SRM, patients interpret symptoms in relation to their mental model of illness and these assessments in turn guide their SMB. Appraisal of the efficacy of their actions serves reinforces or modifies SMB. Thus, in all modules we will work on helping the patient develop accurate perceptual discrimination of symptoms arising from asthma and obesity, thereby creating a process in which patients search for the appropriate signals to initiate and appraise the effects of self-management to generate effective self-regulatory feedback controls. The counselor will also address emotional responses, using normalizing statements (e.g., "Many patients feel that way..."). Finally, we will use strategies to enhance comprehension and retention including teach-to-goal, motivational interviewing, multi-modal communication, and optimized formatting of print materials. To sustain self-regulation, strategies for patients to record, monitor and effectively attribute their outcomes will be reinforced using the aforementioned tools for asthma symptom monitoring in addition to diet and exercise logs.

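### Participants lost to follow-up are to be compared with those retained on three demographics, and no stated method covers permanent drop-out related to asthma severity

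*SAP*

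**What the plan says.** The opening of the SAP's Data Analyses section states that a HIPAA waiver will be obtained in order to "compare non-respondents and those lost to follow-up to study participants by age, gender and ethnicity". Neither document names any other comparison of lost with retained participants. The baseline tests in the same section compare the obesity/onset groups with each other.

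Under Missing Data the SAP writes: "For the outcome assessments, we cannot assume data are missing at random". It then says only that pattern-mixture methods will be considered, and only for an isolated gap in someone who comes back. Multiple imputation is reserved for data taken to be missing at random, with data entry errors as the example. Under Power Calculation: "The estimated power is based on a proposed sample size of 400 with an 80% follow-up rate".

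Under Aim 1 the plan calls for "longitudinal assessment of asthma morbidity measures across four time points (0, 6, 12, and 18 months"). FEV1 is a primary outcome, "and control (ACQ scores); the primary measure of NO metabolism will be L-arginine/ADMA ratio". The growth model is to be estimated by WLSMV. Its predictors include obesity, age of onset and their interaction, with sex, age, comorbidities, depression, allergic sensitization and other baseline covariates as controls.

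**The concern.** One list of three variables serves two different populations. Non-respondents never had a study visit, so demographics may be all that is available for them. People who enrolled and later left have a baseline visit. The protocol keeps data already collected from those who withdraw unless they ask in writing for destruction or refuse its retention (section 3, withdrawal text just before section 4). The values most likely to explain loss, and to reveal whether it is related to outcome, are therefore largely in hand, but no plan to examine them is stated.

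The SAP itself doubts missing at random for outcomes and then gives a remedy that does not reach permanent loss. If people with worse asthma leave more often, later-visit means describe a healthier subset, and a comparison on age, gender and ethnicity may not show it.

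**Working it through.** **Inputs from the documents.** N = 400; 80% follow-up; alpha 0.05; visits at 0, 6, 12 and 18 months (SAP, Aim 1 and Power Calculation).

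**Inputs assumed here**, because the documents give none: loss rates in the worse- and better-controlled halves of 30% vs 10%, or 35% vs 5% (both 20% overall, matching the plan); a normally distributed severity score; a correlation of 0.6 between baseline and 18 months; a correlation of 0.1 to 0.3 between age and ACQ.

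**1. The plan's own figures.** 400 × 0.80 = 320 retained and 80 lost. The stated Aim 1 power (>0.80, RMSEA 0.05 vs 0.03) needs at least 99 degrees of freedom at N = 320, or 71 at N = 400. The model has 34 observed variables, giving 34 × 35 / 2 = 595 covariance moments, so the claim is plausible. It cannot be confirmed because the degrees of freedom are not stated. The point here does not depend on it.

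**2. Shift in the retained mean.** Each half of a standard normal has mean ±0.798.
- 30% vs 10%: the worse-controlled share of those retained is 0.7 / (0.7 + 0.9) = 0.4375. Shift = (2 × 0.4375 − 1) × 0.798 = −0.10 SD at baseline; × 0.6 = −0.06 SD at 18 months.
- 35% vs 5%: the share is 0.65 / (0.65 + 0.95) = 0.406. Shift = −0.1875 × 0.798 = −0.15 SD at baseline; × 0.6 = −0.09 SD at 18 months.

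**3. Effect on group contrasts.**
- Same loss pattern in every group: the shifts nearly cancel. For two groups 0.3 SD apart at baseline (assumed) with 30% vs 10% loss, the contrast bias is 0.003 SD at baseline and 0.002 SD at 18 months. For groups 0.5 SD apart with 35% vs 5% loss, it is 0.006 SD at 18 months.
- Severity-related loss in one group and not in the other: the contrast is biased by the whole shift, about 0.06 to 0.09 SD at 18 months.
- A harsher one-group case: 30% loss in that group, a lost-to-retained baseline difference of about 0.48 to 0.84 SD, and a correlation of 0.5 to 0.7 (all assumed). Simulation gives a bias of about 0.07 to 0.18 SD in that group's 18-month mean.

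**4. What each comparison would detect.** For 80 lost vs 320 retained, SE = √(1/80 + 1/320) = 0.125 SD, so the difference detectable with 80% power is 2.8 × 0.125 = 0.35 SD.
- In the 30% vs 10% case, 0.30 / 0.40 = 75% of those lost are worse-controlled. Their mean is 0.5 × 0.798 = 0.40 SD, so lost and retained differ by 0.40 + 0.10 = 0.50 SD. Comparing ACQ directly has about 98% power.
- Through age, the same difference appears as 0.1 × 0.50 = 0.05 SD to 0.3 × 0.50 = 0.15 SD, with about 7% to 22% power.

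The second line rests wholly on the assumed age correlation. Gender and ethnicity were not calculated.

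**The case against.** The strongest reply is that much of the loss is already handled. Obesity, onset, their interaction, depression and several other covariates are in the growth model, so loss that depends only on those is conditioned on there. That stands. A reader might infer that drop-out related to study group goes unadjusted; for the growth model, the SAP's Aim 1 text contradicts this.

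A reader might also take 0.06 to 0.09 SD as the bias in the comparison of groups. It is a shift in the retained mean, and nearly all of it cancels when the loss pattern is the same in every group.

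It can also be argued that the sentence on the HIPAA waiver lists what the waiver is for, and need not be the whole attrition analysis; likewise, the SAP does not say which variables enter the imputation. That is fair, and the gap is therefore one of specification.

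Nor should a reader infer that complete baseline data exist for everyone lost. Electronic adherence is recorded after each visit and the devices come back later (Protocol, section 8). The timing of the cognitive battery is not given in the documents. Withdrawn participants may have their data destroyed.

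Three things remain. The Kruskal-Wallis comparisons at each visit and the chi-square comparison of adherence carry no covariates and no stated missing-data adjustment. WLSMV is not a full-information estimator, so conditioning on earlier FEV1 or ACQ is not assured. No method is stated for people who do not return.

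**Conclusion.** The point holds as a modest gap in the plan. Loss related to asthma severity is neither examined by any stated comparison nor covered by any stated method, although the SAP doubts missing at random and expects about 80 losses. The likely size is 0.06 to 0.09 SD in the retained 18-month mean, under the assumed loss patterns and a correlation of 0.6. A similar bias in a group contrast requires severity-related loss to be concentrated in one group. The documents give no evidence that this will happen, and they do not support a claim that the Aim 1 contrasts are biased. This is an inexpensive improvement to the analysis and does not threaten the study's validity.

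**What to change.** - Keep age, gender and ethnicity for non-respondents.
- For enrolled participants who are lost, also compare obesity/onset group, site, baseline FEV1, ACQ, L-arginine/ADMA and depression with those retained.
- Impute later outcomes before fitting the WLSMV models, with baseline and earlier-visit FEV1, ACQ and L-arginine/ADMA, and any predictors of loss found above, in the imputation model. For continuous outcomes, full-information maximum likelihood is an alternative.
- Imputation of this kind still assumes missing at random, which the SAP says it cannot assume for outcomes. Add a pattern-mixture or delta-adjusted sensitivity analysis that covers permanent drop-out.

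The cost is a little more analysis and a few sentences in the SAP. No new data are needed.

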*This section always applies, please indicate whether consent will be obtained from subjects. (If not, proceed to the **Waiver or Alteration of the Consent Process** section below). If you will be obtaining consent, describe:*

- *The setting of the consent process.*

Informed consent will take place either in person or over the phone in a space that safeguards confidentiality.

- *Describe any waiting period available between informing the prospective subject and obtaining the consent.*

The participant will have as much time as needed to review the consent.

- *If you will be following "[SOP HRP-090 Informed Consent Process for Research](#)", after addressing the points above, indicate this. Otherwise, also describe:*
 - *The role of the individuals listed in the application as being involved in the consent process.*
 - *The time that will be devoted to the consent discussion.*
 - *Steps that will be taken to minimize the possibility of coercion or undue influence.*
 - *Steps that will be taken to ensure the subjects' understanding.*
 - *Describe any tools that will be utilized during the consent process*

The team will adhere to "SOP-HRP-090 Informed Consent Process".

-

Non-English Speaking Subjects (See PPHS policy)

Indicate what language(s) other than English are understood by prospective subjects or representatives. If subjects who do not speak English will be enrolled, describe the process to ensure that the oral and written information provided to those subjects will be in that language. If you intend to exclude potential participants who do not speak English, provide a justification for doing so.

Spanish-speaking participants will be enrolled. All study materials have been translated into Spanish and back-translated by study team members who are fluent in Spanish. The study team contains a Research Coordinator who is fluent in Spanish and will administer the study visits in Spanish to Spanish-speaking participants.

This study will exclude participants who do not speak English or Spanish as the study team is not equipped to administer the study visits in languages other than English or Spanish.

 Mount Sinai	Protocol Name:	Obesity and Asthma: Unveiling Metabolic and Behavioural Pathways
	Principal Investigator:	[name], DrPH
	Primary Contact Name/Contact Info:	[name] / [contact] / [contact]
	Date Revised:	1/25/21
	Study Number:	STUDY-16-00079

Waiver or Alteration of the Consent Process

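### The language check uses MIMIC models, which hold item loadings equal in English and Spanish, so a clean result cannot by itself support calling a scale invariant

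*SAP*

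**What the plan says.** The SAP's plan for language, under Data Analyses (Measurement Invariance), is one sentence: "We will determine whether the key measures are invariant across language using multiple indicator multiple cause models". It names no language-by-factor interaction, no two-group factor model, no level of invariance (configural, metric, scalar) and no action if a scale fails.

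The sentence before it covers structure but does not mention language: "We will examine the factor structure of key measures (e.g., MARS) and the multi-component structure of the IPQ and BMQ". The SAP does plan to let parameters differ between groups, but only for sex, under Aim 1: "we will repeat the analyses freeing the parameters to differ by gender".

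The Protocol (section 9, Non-English Speaking Subjects) confirms that Spanish speakers enter and describes the translation: "All study materials have been translated into Spanish and back-translated by study team members who are fluent in Spanish". It gives no expected number or share of Spanish interviews.

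The scales matter chiefly in Aim 2: "Asthma and obesity beliefs will constitute a latent variable consisting of two constructs: a) disease beliefs (measured with the IPQ", with the BMQ measuring the second construct. Their relation to self-management behaviour (SMB) is then modelled: "We will assess the potential influence of cognition and illness beliefs on SMB separately then test a full model".

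**The concern.** Invariance across language has at least two parts. Items must start from the same level in both languages (intercepts or thresholds), and they must track the construct equally strongly (loadings). The named model tests the first part and assumes the second.

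A translated item can read correctly and still relate more weakly to its construct. Back-translation checks wording; it does not test loadings. Such an item may pass a MIMIC check, and the scale would then be reported as invariant although loadings had never been examined. What is at stake is the warrant for that statement, on which pooling English and Spanish answers in the Aim 2 belief models partly rests.

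**Working it through.** **No plan figure to reproduce.** The SAP attaches no power, alpha or sample size to the invariance check. Its power paragraph gives the overall size: "The estimated power is based on a proposed sample size of 400 with an 80% follow-up rate", so 400 × 0.80 = 320 at follow-up. The simulations use 400, the more favourable number.

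**Step 1: what the model can see.** For item j and language x (0 English, 1 Spanish), a standard MIMIC model is

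y_j = ν_j + λ_j η + β_j x + e_j, with η = γ x + ζ.

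Language enters through γ (difference in latent mean) and β_j (shift in item intercept). There is a single λ_j, so no parameter lets a loading differ.

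**Step 2: why the intercept test reacts weakly.** If the Spanish loading is λ_S and the latent means differ by δ, the item mean is displaced by about (λ_S − λ)δ relative to the English loading.
- Loading 0.7 to 0.3, δ = 0.3 SD: (0.3 − 0.7) × 0.3 = −0.12.
- Loading 0.7 to 0.5, δ = 0.3 SD: (0.5 − 0.7) × 0.3 = −0.06.
- δ = 0: no displacement, so the direct-effect test has nothing to find.

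**Step 3: simulation, five items.** Assumed, since the documents give none of these: continuous items, English loadings 0.7, one weak Spanish item, δ = 0.3 SD. Two-group maximum likelihood, likelihood-ratio tests with 1 df at the 5% level, 100 to 150 simulated trials per setting. Ranges span repeated runs.

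| Spanish speakers (of 400) | Direct effect, loading 0.30–0.35 | Loading test, loading 0.30–0.35 | Loading test, loading 0.5 |
|---|---|---|---|
| 20 (5%) | 8–13% | 43–53% | 23–25% |
| 40 (10%) | 12–23% | 73–85% | 27–28% |
| 80 (20%) | 14–19% | 88–99% | 46–57% |

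Under true invariance the direct-effect test rejects in 3–7% and the loading test in 4–6%. With 100 trials, the simulation standard error at a rate of 50% is √(0.5 × 0.5/100) = 5 points. Rounded, the three result columns are roughly 10–25%, 45–99% and 25–55%.

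**Step 4: a harsher setting.** Six items, two of them at 0.3 in Spanish, 400 simulated trials, Spanish shares of 10%, 20% and 30%.
- Equal latent means: the MIMIC omnibus direct-effect test rejects in 6.5%, 7.5% and 6%, and the overall MIMIC chi-square in 7.8%, 7.3% and 8.5%. Both are close to the false-positive rate. A two-group equal-loadings test rejects in 77%, 96% and 99%.
- Latent means 0.5 SD apart: the MIMIC omnibus test rejects in 25%, 34% and 34%, and would label the problem an intercept shift. The equal-loadings test rejects in 77%, 95% and 99%.

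**Step 5: does a missed item distort the Aim 2 path?** Population-level bias in the pooled belief-to-behaviour path, assuming the same true path in both languages and otherwise equal residual structure:
- One of five items at 0.3, 5–20% Spanish: 0.0% for the standardised latent path, under 1% with a sum score.
- Two of six at 0.3, up to 30% Spanish: about 0.1% latent, 2% sum score.
- Three of five weak, 20% Spanish: 0.7% latent, about 3% sum score.

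The exception is a weak item that also sets the factor's scale. The pooled loading is then about 0.7 − 0.4f at Spanish share f: 0.68 at 5% and 0.62 at 20%. The unstandardised path inflates by 0.7/0.68 = 1.03 to 0.7/0.62 = 1.13, or 3–13%. The standardised path does not move.

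**The case against.** The strongest reply is that MIMIC is a sensible choice when one language group is small, and that the SAP sentence does not rule out an extended MIMIC with a language-by-factor term. Both are true. A plain MIMIC analysis is defensible if only intercept bias is claimed, and naming the extension would meet the point. As written, however, the SAP names only the model class and promises a verdict on invariance.

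Second, the better test is no cure. For a moderate fall in loading (0.7 to 0.5) it misses most cases at 20 or 40 Spanish speakers and about half at 80. These rates are for a single known item, without correction for testing every item. This stands, and is why intervals matter more than pass or fail.

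Third, the items may be ordinal and analysed with the weighted least squares estimator that the SAP names for Aim 1. The rates would then change, but the equal-loading constraint would not.

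A reader might also infer that an undetected item would distort the belief paths and so misdirect the pilot counselling, which targets the beliefs most strongly linked to poor self-management. The documents give no figure to support that. In the scenarios above the standardised latent path moves by less than 1%, too little to be likely to reorder a ranking.

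**Conclusion.** The stated method cannot deliver the stated conclusion. A standard MIMIC model assumes equal loadings, and nothing else in the SAP tests loadings by language. That holds whatever the number of Spanish speakers.

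The size rests on assumed values. With one of five Spanish loadings falling to about 0.3 and 20 to 80 Spanish speakers, the planned test flags the item in roughly 10–25% of trials, against about 45–99% for a loading test. It would be too strong to say that MIMIC nearly always misses: with latent means 0.5 SD apart its omnibus test rejects in 25–34%, though under the wrong label.

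The reach is limited to the verdict on translated questionnaires used chiefly in Aim 2 (IPQ, BMQ, MARS). FEV1, the L-arginine/ADMA ratio, electronically measured adherence and accelerometer data are unaffected. The calculations do not show material harm to the pooled standardised belief paths, so this is a correction to make the claim match the test, not a threat to the main results.

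**What to change.** In the Measurement Invariance sentence of the SAP:

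1. For each item, test both the direct language effect (intercept or threshold) and the language-by-factor interaction (loading). If enough Spanish speakers enrol, a two-group configural, metric and scalar sequence may replace this.
2. Report each difference with its confidence interval, and call a scale invariant only if both parts are small. Otherwise limit the statement to absence of intercept bias.
3. If an item is flagged, repeat the Aim 2 models without it as a sensitivity analysis. Freeing its loading by language throughout the growth models is not needed. It would carry an interaction, or a separate small group, through a model that the SAP puts at 13 latent variables.

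No new data are needed. The costs are more item-level tests, wide intervals if few Spanish speakers enrol, and a separate maximum-likelihood run for the interaction.
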